### 8.4 Device storage and supply

The funder Carl Zeiss will supply both Monofocal non-Toric IOLs and Toric IOLs required for this study free of charge to the REI of the UHP. The PI will have a specific order portal from Carl Zeiss to order IOLS according to pre-surgery assessment data. The IOLs will then be sent to REI directly and handled in similar way as other IOLs used in cataract surgery. The IOLS will be stored as recommended on the packaging and requires nothing different than any other brand of IOLs used at the REI.

All individual IOLs are supplied sterile, non-pyrogenic in its own sterilization pouch. Sterility is assured provided the sterilization pouch seal has not been compromised or the pouch has not been punctured.

### 8.5 Preparation and labelling of device

The PI and his ophthalmologist team are responsible for calculating the IOL power and select the specific IOL as indicated on the individual IOL packaging. The preparation of the IOLs used in this study will be the same as other IOLs used in routine cataract lens replacement surgery.

The surgeons (PI and his team) need to check the label on the lens box for proper lens model, dioptric power and expiration date. After verification of the dioptric power of the lens after opening, the lens will be removed from the pouch and transfer in a case to a sterile environment. Prior to the actual folding process, the lens should be handled by the haptic portion only. The lens needs to be rinsed thoroughly using sterile intraocular irrigating solution. Then, the lens can be oriented for insertion.

Vision and balance changes after bilateral implantation of Toric IOLs  
IRAS ID: 286913

## **8.6 Cataract schedules**

Each eye will be implanted with one IOL in the capsular bag and two separate occasions. PI reported at the time of writing this protocol, the second eye cataract surgery would be scheduled at around four months after the first eye surgery.

Orientation of the IOLs will be checked before and after implantation of IOLs by the ophthalmologists as part of routine care. The PI has extensive experience using Toric IOLs for cataract surgery, they communicated that the cataract surgery using Toric IOLs usually took five to eight more minutes because it took longer time to put in and to ensure the axis of the lenses were in a precise position for correction of astigmatism.

Vision and balance changes after bilateral implantation of Toric IOLs  
 IRAS ID: 286913

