### 3. OBJECTIVES AND OUTCOME MEASURES/ENDPOINTS

#### 3.1 Primary objective

The objective of the study is to compare the effects of Toric intraocular lens versus Monofocal intraocular lens replacement on dynamic stability among cataract patients with astigmatism using a randomised controlled trial.

It is hypothesized that Toric intraocular lens will have additional correction of astigmatism after the cataract surgery resulting in and better outcomes in dynamic stability and higher chance of “spectacle-free”.

There are two arms of the trial: Monofocal Toric intraocular lens versus Monofocal non-Toric intraocular lens

The research question is based on the PICOT criteria:

P Population	Cataract patient with astigmatism >1.0DD awaiting intraocular lens replacement surgery
I Intervention	Monofocal Toric intraocular lens
C Comparison group	Monofocal non-Toric intraocular lens
O Outcome of interest	Primary- Dynamic stability will be measured by motion sensor during functional movements (crossing obstacles, turning and stair walking)  Secondary- Eye tracking characteristics, visual function, risk of fall, vision specific quality of life questionnaire and Toric IOL rotation.
T Time	Before operation (T1) and 3-6 months after each eye operation (T2, T3)

Vision and balance changes after bilateral implantation of Toric IOLs  
IRAS ID: 286913

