### 3.6 Table of endpoints/outcomes

Objectives	Outcome Measures	Timepoint(s) of evaluation of this outcome measure (if applicable)

Primary Objective To compare dynamic stability in cataract patients with Toric versus non-Toric IOLs
	
Dynamic stability: - movement of centre of mass and head tilting using wireless motion sensors.
	
Three timepoints:
 
 
1. pre-operation study visit and
 
2. post-operation study visit (3-6 months after first eye surgery).
 
3. post-operation study visit (3-6 months after second eye surgery).
 

Second Objectives To compare eye tracking characteristics, visual functions, risk of falls and quality of life in cataract patients with Toric versus non-Toric IOLs
	
Eye tracking characteristics: -area of interest by gaze pattern -Gaze duration on area of interest
 
Vision function include visual acuity, IOL rotation by degrees of rotation from intended position and degree rotation from the steepest meridian using special optometry equipment to look at the front of the eye (digital slit lamp and Pentacam)
 
Risk of fall will be measured by fear of falling and fall efficacy scale questionnaires. Vision related quality of life will be measured by CAT-PROM5 questionnaire.
	
Three timepoints:
 
 
1. pre-operation study visit and
 
2. post-operation study visit of first eye at 3-6 months after the surgery
 
3. post-operation study visit of second eye at 3-6 months after the surgery
 

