## 7.7 Trial assessments

Three study visits will be arranged for each participant who have given written informed consent to take part in the study.

**Study visit 1:** Pre-surgery baseline assessment will take place at the PAHC building of UoP, at least one week before the cataract surgery. After the participants have the cataract screening appointment at REI, they usually wait 3 to 6 weeks before the cataract surgery. The first study visit for the pre-operation baseline assessment will be arranged during this period. This also gives participants extra time to reconsider taking part in the study from when they signed the informed consent form at the REI. The study coordinator will reconfirm informed consent over the phone or by email (whichever is the preferred contact method) with the participant before arranging the first study visit and at the start of each study visit. If a participant needs to delay or cancel the cataract surgery due to a medical reason, the study coordinator will liaise with the PI who is the Ophthalmologist to confirm the participant is still suitable to take part in the study.

Intervention: participants will be randomized into two groups. One group will receive Toric Monofocal IOLs and the other group will receive standard non-Toric Monofocal IOLs.

**Study visit 2:** Reassessment of outcome measures will take place three to six months after first eye surgery at the PAHC building of UoP.

**Study visit 3:** Reassessment of outcome measures will take place three to six months after second eye surgery at the PAHC building of UoP.

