### **10.2 Planned recruitment rate**

140 participants will be recruited over three-year period (minimal sample size of 110 plus 20% drop out rate estimation)

According to latest data from the National Ophthalmology audit database by the Royal College of Ophthalmologists, the REI of UHP performed 2525 cataract between 1st of September 2018 to 31st August 2019. The PI who performed cataract surgery at the REI reported around 3000 cataracts surgery were performed last year and the number is estimated to be similar this year. Due to COVID, there were longer waiting list and the waiting time between first and second cataract surgery at UHP has increased to about 4 months.

Approximately 40% patients undergo cataract surgery on both eyes (Jaycock, 2009 #281) (Day, 2015 #282). Among patients eligible for cataract surgery in NHS, 42% were reported to have mild to moderate astigmatism ( $>1.0$  D) (Day, 2019 #283). Therefore, it is estimated about 500 patients at REI annually will meet the inclusion criteria (needing cataract surgery in both eye with mild-moderate astigmatism) and our target for 140 participants out of the potential 1500 patients over three year

Vision and balance changes after bilateral implantation of Toric IOLs  
IRAS ID: 286913

should be a feasible number (10% of potential eligible patients), especially with the increasing number of cataract surgeries done every year.

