### 10.3.2 Primary outcome analysis- Dynamic stability in three functional activities

The following outcomes will be collected at three time points: before surgery, 3 to 6 months after first and second eye surgery.

Outcome measures	Data collected	Data type/ details	Quantitative Statistical Analysis
Dynamic stability during turning, obstacle crossing and stair walking	Accelerometers data (angular position and acceleration) of change in head tilting and centre of mass will be recorded  Performance of TU&G test	Interval  Centre of mass and head movement will be calculated using ProMove 3D (Inertia Technology, The Netherlands) and MATLAB.  The angular position, velocity and acceleration of the sensors will be tracked on each participant  Duration in seconds of TU&G test	The average reading of the 3 trials in each functional activity will be calculated.  Mixed ANOVA and post-hoc Bonferroni tests will be used to determine the differences between the Toric IOLs group and Monofocal IOLs group before surgery and 6 months after second eye surgery.

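### Visit 2 may fall up to 6 months after the first eye while second-eye surgery is expected at about 4 months, so the after-first-eye (T2) results can mix one-eye and early two-eye states

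*Combined protocol and SAP*

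**What the plan says.** Section 7.7 sets visit 2 as follows: "Reassessment of outcome measures will take place three to six months after first eye surgery at the PAHC building of UoP". The PICOT table in section 3.1, the endpoint table in section 3.6 and section 10.3.2 give the same window. Section 3.6 lists this visit for the primary and the secondary outcomes, and the schedule in Appendix 2 heads it as follow-up after the first eye. Visit 3 has a window of the same length counted from the other operation: "Reassessment of outcome measures will take place three to six months after second eye surgery at the PAHC building of UoP".

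The interval between the operations is stated twice. Section 8.6 says that "the second eye cataract surgery would be scheduled at around four months after the first eye surgery", and section 10.2 says that "the waiting time between first and second cataract surgery at UHP has increased to about 4 months".

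On analysis, section 10.3.2 collects the primary outcome at three time points, but the comparison it describes is of the Toric group with the "Monofocal IOLs group before surgery and 6 months after second eye surgery". Section 10.3.3 uses the same contrast for eye tracking, vision and questionnaires. Section 10.3 describes the within-subjects factor as time with two levels, before and after surgery, without saying whether visit 2 counts as after.

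**The concern.** T2 is labelled and tabulated as the state after the first operation. With the second operation at about month 4, only the first month of the three-month visit 2 window reliably precedes it. A participant seen in months 4 to 6 would be 0 to 2 months past the second operation. That is not a one-eye state, and it is earlier than the 3 months the protocol itself allows before assessing a second-eye result.

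At stake is what T2 can be said to show. If some participants have one operated eye and others two, the T2 summaries for balance, gaze, acuity, fear of falling and quality of life cannot be read as first-eye results, and a change from T2 to T3 cannot be read as the contribution of the second lens. If visit 2 is fitted as part of the post-surgery level in the mixed ANOVA, the same mixture enters that model. Eye status at the visit cannot be altered afterwards, and unless it is recorded it cannot be separated in the analysis.

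**Working it through.** **Inputs from the documents.** Visit 2 window: months 3 to 6 after the first eye (sections 3.1, 3.6, 7.7, 10.3.2). Second-eye surgery: about month 4 (sections 8.6, 10.2). Visit 3 window: 3 to 6 months after the second eye (section 7.7). Sample size: effect size 0.25, alpha 0.05, power 85%, 55 per group, 70 with 20% dropout (sections 3.3, 10.1).

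**Step 1: does the plan's sample size depend on visit 2?** For the between-group test in a repeated-measures ANOVA, the noncentrality is λ = f²·N·m / (1 + (m − 1)ρ), with 1 and N − 2 degrees of freedom, where m is the number of time points and ρ their correlation. The plan does not state ρ.
- m = 2, ρ = 0.5 (assumed): λ = 0.0625 × 110 × 2 / 1.5 = 9.17. Power is 0.851 and N = 110 is the smallest total reaching 85%, so the stated 55 per group is reproduced.
- m = 2 with ρ = 0.3 or 0.7 gives 48 or 63 per group.
- m = 3 with ρ = 0.5 gives 49 per group. Three time points give the same λ as the first case only at ρ = 0.625: 0.0625 × 110 × 3 / 2.25 = 9.17.
- Dropout: 55 / 0.8 = 68.75, so 69; the plan uses 70.

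The figure therefore agrees with a two-time-point calculation, which is also how sections 10.3 and 10.3.2 describe the comparison. It does not prove that visit 2 was left out, because ρ is unknown.

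**Step 2: how much of the visit 2 window lies after second surgery?** With second surgery at month s and visits spread evenly over months 3 to 6 (an assumption), the share is (6 − s) / (6 − 3).

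| Second surgery (month) | Share of visit 2 after it |
|---|---|
| 3.5 | 2.5 / 3 = 83% |
| 4 | 2 / 3 = 67% |
| 4.5 | 1.5 / 3 = 50% |
| 5 | 1 / 3 = 33% |
| 5.5 | 0.5 / 3 = 17% |
| 6 or later | 0% |

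At month 4, 67% is about 73 of 110 completers. If second-surgery dates vary normally around month 4 with a standard deviation of 0.25 to 1.5 months (assumed), a simulation gives 67% down to 61%.

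**Step 3: how close can visits 2 and 3 come?** With second surgery at month 4, visit 3 opens at month 4 + 3 = 7. A visit 2 at month 6 is within its window, follows the second operation by 2 months, and may precede visit 3 by one month, with both eyes operated on at both visits.

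**Step 4: does any other text remove the overlap?** None was found. Sections 3.6, 7.7 and 10.3.2 and Appendix 2 set no order between visit 2 and the second operation, and none says how a visit after that operation is labelled or analysed. Sections 7.8 and 10.6 allow two further contact attempts within two months of a missed visit, so a visit first booked in month 3 or 4 can drift past the second operation.

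**The case against.** The strongest reply is that no written efficacy contrast names visit 2. Sections 10.3.2 and 10.3.3 compare the arms before surgery and after the second eye, and the objectives in sections 3.1 and 3.2 concern Toric versus non-Toric lenses in patients having both eyes done, not the effect of the first lens or the change from T2 to T3. This stands. A reader might infer that the primary result is compromised or the trial underpowered; the documents do not support that. Because each participant is assigned one lens type for both eyes, a comparison of arms at T2 also remains a randomised comparison. What it loses is its reading as a one-eye comparison.

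A reader might also infer bias between arms at T2. That would need the timing of the second eye to differ by arm, and nothing in the documents says it does: Appendix 2 refers to the routine surgical schedule without distinguishing arms. Section 2.1 notes that repositioning applies only to Toric lenses, and section 10.4 regards further surgery as very likely after rotation above 5 degrees, but neither says that this delays the second eye.

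The size is also open to challenge, and this stands too. Four months is approximate, was reported when the protocol was written, and is linked in section 10.2 to longer waiting lists. The trial summary gives a treatment duration of up to 12 months after the first eye, which leaves room for longer intervals. Staff could book most visits in months 3 to 4. The percentages are therefore illustrations, not forecasts.

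Finally, the trial flow chart could not be read and the CRF is not among the documents. The flow chart may show an order of events, and the CRF may already hold the surgery dates.

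**Conclusion.** The concern holds in a limited form. On the plan's own figures the visit 2 window runs past the expected second operation, and no readable text prevents a visit 2 after it. T2 can therefore mix one-eye and early two-eye states for every outcome collected there. That overlap needs no assumption beyond the stated window and the stated interval. The share affected does: 67% rests on even booking and second surgery at month 4, and plausible alternatives run from 83% to 0%. The direct consequence is confined to the T2 results and to any model in which the post-surgery level of section 10.3 includes visit 2. The written primary and secondary contrasts and the planned 140 participants are not directly affected.

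**What to change.** Reconcile the visit 2 window with the interval between operations, leaving surgical scheduling as it is.

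- In sections 3.6 and 7.7, book visit 2 at least 3 months after first-eye surgery and before second-eye surgery, with a date check at booking.
- Record both surgery dates, and the number of operated eyes at visit 2, if the CRF does not already do so.
- In section 10.3, say whether visit 2 is part of the post-surgery level. In any analysis using T2, count only assessments made before second-eye surgery as after first eye, and report the others separately.
- In section 10.6, state that a T2 missed or relabelled for this reason does not trigger withdrawal and discarding of data, so that the participant stays in the primary contrast.

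The last item matters because the usable window shrinks to about 4 − 3 = 1 month at current waiting times, which cannot hold the two-month recontact process. Some T2 values will be missing; the documents do not allow a count. Otherwise the cost is a few sentences and a date check per participant, with no change to the sample size.

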## 9. SAFETY REPORTING

### 9.1 Definitions

Term	Definition
Adverse Event (AE)	Any unfavourable sign, symptom, or disease in a participant, regardless of severity and regardless of cause.
Adverse Device Effect (ADE)	All untoward and unintended responses to a medical device. The phrase "responses to a medical device" means that a causal relationship between the device under investigation and an AE is at least a reasonable possibility, i.e., the relationship cannot be ruled out. All cases judged by either the reporting medically qualified professional or the sponsor as having a reasonable suspected causal relationship to the device qualifies as a device effect. This also includes any event resulting from insufficiencies or inadequacies in the instruction for use or deployment of the device and includes any event that is a result of a user error.
Serious Adverse Event (SAE)	
A Serious Adverse Event (SAE):
 
 
• results in death
 
• is life-threatening*
 
• requires inpatient hospitalisation or prolongation of existing hospitalisation**
 
• results in persistent or significant disability/incapacity
 
• is a significant or important medical event
 
 
*The term "life-threatening" in this context refers to an event in which the participant was at risk of death at the time of the event; it does not refer to an event which hypothetically might have caused death if it were more severe.
 
**Hospital admissions for elective procedures will not be reported as SAEs. All unplanned hospital admissions will be reported as SAEs, regardless of duration of hospital stay. This includes visits to ED departments.
 
NOTE Device deficiencies that might have led to a serious adverse event where a suitable action had not been taken or an intervention had not been made or if circumstances had been less fortunate are handled under the serious adverse event reporting system.

Suspected Serious Adverse Device Effect (SADE) / Serious Adverse Reaction (SAR)	
An Suspected Serious Adverse Device Effect (SADE)/ Serious Adverse Reaction (SAR) which has previously been identified in the study protocol that results in:
 
 
• Death
 
• Life threatening illness or injury
 
• Hospitalisation or prolongation of existing hospitalisation.
 

Vision and balance changes after bilateral implantation of Toric IOLs  
IRAS ID: 286913

	
 
• Persistent or significant disability or incapacity.
 
• Foetal distress, foetal death or congenital anomaly or birth defect.
 
• Is otherwise considered medically significant by the Investigator
 
 
All cases judged by either the reporting medically qualified professional or the sponsor. Any hospitalisation planned prior to enrolment is not a SADE.

Unanticipated Serious Adverse Device Effect (USADE)	
Any serious adverse device effect on health or safety or any life-threatening problem or death caused by, or associated with a device, if that effect, problem, or death was not previously identified in nature, severity, or degree of incidence in the study protocol or application (including a supplementary plan or application), or any other unanticipated serious problem associated with a device that related to the rights, safety or welfare of the subject.

## 9.2 Responsibilities

A sponsor or investigator may take appropriate urgent safety measures in order to protect research participants against any immediate hazard to their health or safety, without prior authorisation from a regulatory body.

The CI takes primary responsibility for the conduct of this study. They will also lead and manage all investigators of this study and coordinate with the sponsor. They are responsible for the adherence and implementation of safety reporting relating to the study visits at the UoP (PAHC building).

The PI is responsible for management of the participant recruitment and clinical interventions at the UHP site. The PI is also responsible for the adherence and implementation of safety reporting relating to the cataract surgery, clinical care or at the site of REI of Derriford Hospital and for coordination with CI.

## 9.3 Reporting of AEs and ADEs

Only the following AE's occurring during the study, observed by the investigator or reported by the participant will be recorded on the CRF.

- AE's related to the treatment, but not including well known side effects due to eye drops such as blurriness.
- AE's associated with falls.

Vision and balance changes after bilateral implantation of Toric IOLs  
IRAS ID: 286913

The following information will be recorded: description, date of onset and end date, severity, assessment of relatedness to device, other suspect drug or device and action taken. Follow-up information should be provided as necessary.

The relationship of AEs to the device will be assessed by a medically qualified investigator and will be followed up until resolution, or the event is considered stable. Any events continuing at the end of the study will be followed up by the participants GP and/ or the routine clinical care team until discharge. This will apply to participants who withdraw from the study.

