### **7.4 Blinding**

The participants will be masked to the interventions prior to the surgery. They will be told which IOLs they received at the end of their final visit. The CI will conduct the simple randomization for the participants through the random.org and he will be masked to the outcome assessment. The randomized list of participants will be passed to the PI and his ophthalmologist team to prepare the IOLs and deliver the

Vision and balance changes after bilateral implantation of Toric IOLs  
IRAS ID: 286913

cataract correction surgery. So, the PI cannot be masked to the intervention, but he is masked to the outcome assessment.

The outcome assessors for study visits will be masked to the interventions given to the participants. In the post-surgery study visit, the outcome assessors will carry out the dynamic stability reassessment before any visual assessment to ensure they are still masked to the primary outcome measures as the visual assessment will reveal which types of the IOLs the participants received.

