#### **9.4 Recording and reporting of SAEs, SADEs and USADEs**

This study uses CE marked devices and is not regulated by the Medicines and Healthcare products Regulatory Agency (MHRA). All SAE/SADE/UADEs need to be reported to the sponsor R&D **within one working day** of the investigator team becoming aware of them. The Chief Investigator will assess the event for expectedness using the current study protocol, see section 9.5 Known (expected) complications associated with Toric IOL surgery.

Reports of related and unexpected SAEs/ SADE's should be submitted by the Sponsor to ethics within 15 days of the Chief Investigator or Principal becoming aware of the event, using the SAE report form for non-CTIMPs published on the HRA website.

All reporting to R&D should be by e-mail the Research Governance Manager (RGM) or their Deputy giving as much information about the incident as possible.

The RGM will undertake an initial review of the information. Events will be followed up until resolution, any appropriate further information will be sent by the research team in a timely manner. Any events continuing at the end of the study will be followed up by the participants GP and/ or the routine clinical care team until discharge. This will apply to participants who withdraw from the study.

Reporting to the Manufacturer will be done in liaison with the Chief Investigator.

The Manufacturer has a legal obligation to report all events that need to be reported to the Nominated Competent Authority immediately (without any unjustifiable delay) if a link is established between the event and the device, but no more than:

Vision and balance changes after bilateral implantation of Toric IOLs  
IRAS ID: 286913

- 2 days following the awareness of the event for Serious Public Health Threat.
- 10 days following awareness of the event for Death or unanticipated serious deterioration in health.
- 30 days following the awareness of the event for all other event meeting the SAE criteria.

In the event of an accident, incident or near miss relating to cataract surgery or clinical care or happens at the Derriford Hospital, in addition to previous reporting requirements, the recording and reporting should follow the Incident Management Policy of the University Hospitals of Plymouth NHS Trust. The PI or need to report *via* UHP Datix and notify the CI and Sponsor.

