### **13.9 Indemnity**

This is an NHS-sponsored research study. If an individual suffers negligent harm as a result of participating in the study, NHS indemnity covers NHS staff and those people responsible for conducting the trial who have honorary contracts with the relevant NHS Trust. In the case of non-negligent harm, the NHS is unable to agree in advance to pay compensation, but an *ex-gratia* payment may be considered in the event of a claim.

The PI is an ophthalmologist, and all co-investigators are allied health professional, they all have their additional professional liability insurance with their professional governing body for clinical negligence and public liability insurance.

If a SAE happens during any of the three study visits (on the University site), it has to be reported formally to the study CI, [name], to assess the seriousness and causality, if deemed to be serious it must be reported to the Study Sponsor within 24 hours and would trigger a Serious Incident Requiring Investigation (SIRI) by the University. Additionally, the Optometry department of the UoP is responsible for any insurance claim regarding loss or damage to equipment used in the three study visits at their campus.

Vision and balance changes after bilateral implantation of Toric IOLs  
IRAS ID: 286913

UoP has in force an insurance for Professional Negligence indemnity for research and consultancy service. It also has in force an employer's and public liability insurance to cover activities on campus.

<https://www.plymouth.ac.uk/about-us/university-structure/service-areas/procurement/insurance-certificates>

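### Section 9.3 enters non-serious, non-fall adverse events on the CRF only if they are judged treatment-related, and those placed to judge can know the lens

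*Combined protocol and SAP*

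**What the plan says.** - **Definition (9.1).** An adverse event is "Any unfavourable sign, symptom, or disease in a participant, regardless of severity and regardless of cause".
- **What is recorded (9.3).** "Only the following AE's occurring during the study, observed by the investigator or reported by the participant will be recorded on the CRF". Two items follow: "AE's related to the treatment, but not including well known side effects due to eye drops such as blurriness" and "AE's associated with falls".
- **Who judges relatedness (9.3).** "The relationship of AEs to the device will be assessed by a medically qualified investigator". Relatedness to the device is also one of the items to be written down for each recorded event.
- **Who knows the lens (7.3, 7.4, 7.5).** The principal investigator holds the list and operates, and 7.4 accepts that "the PI cannot be masked to the intervention". The chief investigator generates the allocation and, according to 7.5, holds the list. Section 7.4 also says that the post-operative visual assessment discloses the lens type to the outcome assessors.
- **Serious events (9.4).** "All SAE/SADE/UADEs need to be reported to the sponsor R&D", within one working day.
- **Serious events at study visits (13.9).** These go to the chief investigator "to assess the seriousness and causality, if deemed to be serious it must be reported to the Study Sponsor within 24 hours".
- **Analysis source (11.1).** The statistical analysis uses the CRF data.

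**The concern.** A recording rule that depends on cause moves the causal judgement ahead of the data. An event that someone thinks unrelated to treatment is not entered, so it cannot be reclassified or counted later. In a two-arm trial this matters if the person deciding knows the arm. The same complaint could then be attributed differently in the two groups, and the recorded counts could differ when the true rates do not, or agree when they do.

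The events most exposed are mild and open to interpretation. Section 9.5 lists several, such as glare, halos and dry eye. The trial has some use for complication data: section 10.4 expects its rotation subgroup to inform on surgical complications, and Appendix 1 names surgical complication as a key risk to monitor. A final report would normally show adverse events by arm as well.

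**Working it through.** The check is mainly textual. The plan gives no adverse event rate, safety margin or safety power, so there is no planned figure to reproduce.

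**Step 1: which events face the filter?**

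| Event | Causal judgement needed before it is recorded? | Source |
|---|---|---|
| Fall-associated event | No | 9.3, second item |
| Serious event | Not for reporting to the sponsor; whether an unrelated one also reaches the CRF is not stated | 9.4 |
| Non-serious, non-fall event | Yes, it must be related to treatment | 9.3, first item |

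The filter acts on the last row. Section 9.3 provides no log of events that were considered and left out.

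**Step 2: who could apply it, and do they know the lens?** Section 9.3 says that events may be observed by the investigator or reported by the participant. It does not say who decides that an event qualifies. The candidates are:

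- *Principal investigator.* Section 13.9 describes this person as an ophthalmologist and all co-investigators as allied health professionals. Unmasked (7.3, 7.4). The ophthalmology team also receives the list (7.4).
- *Chief investigator.* A registered optometrist according to the Risks text in 2.1. Knows the allocation (7.3, 7.5).
- *Outcome assessors.* Masked during the mobility tests, but not once the visual assessment has been done (7.4), which is also when many eye findings would emerge.

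No candidate is reliably masked when an ocular event is likely to be judged.

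**Step 3: do the sections on serious events agree?** Section 9.3 gives relatedness to the device to a medically qualified investigator. Section 13.9 gives causality and seriousness of visit events to the chief investigator, who is an optometrist. Section 9.4 sets one working day for reporting to the sponsor, and 13.9 sets 24 hours. Neither pair matches.

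**Step 4: illustration of size, on assumed rates only.** Let the true rate of such events be p in both arms, and let fractions q1 and q2 of them be recorded. The recorded rates are p × q1 and p × q2. Take 70 per arm (10.1), all followed, and a two-sided 0.05 test. The chance of a falsely significant excess in the arm with fuller recording is Φ((d − 1.96 × SE0) / SE1), where d is the recorded difference and SE0 and SE1 are the pooled and unpooled standard errors.

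For p = 20%, q1 = 90% and q2 = 70%, the recorded rates are 18% and 14%, so d = 0.04. SE0 = √(2 × 0.16 × 0.84 / 70) = 0.0620 and SE1 = √((0.18 × 0.82 + 0.14 × 0.86) / 70) = 0.0619. The result is Φ(−1.32) = 9%, against 2.5% with equal recording.

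| Assumed p | 90% v 70% recorded: difference, chance | 90% v 50% recorded: difference, chance |
|---|---|---|
| 10% | 2 points, 6% | 4 points, 15% |
| 20% | 4 points, 9% | 8 points, 27% |
| 30% | 6 points, 13% | 12 points, 41% |
| 40% | 8 points, 17% | 16 points, 56% |

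Nothing in the documents shows that recording would differ between arms, or in which direction. The table says only what would follow if it did.

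**The case against.** The strongest reply is that limited recording can be a proportionate choice for CE-marked lenses used as intended, and that a broad definition in 9.1 with a narrower recording scope in 9.3 is not a contradiction. That stands: the point is a design weakness, not an inconsistency between 9.1 and 9.3.

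The filter also refers to treatment, not to the device. Appendix 2 labels the treatment phase as routine cataract surgery and care. If treatment includes the operation, an event blamed on surgery qualifies in both arms, and there is less room for differential recording. The protocol does not define the term, so this reading is possible but not secured. In addition, visual acuity, refraction, tilt and decentration are measured as outcomes, with rotation in the Toric arm, so some lens problems are captured without an adverse event entry.

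A reader might infer three stronger things that the documents do not support:

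- *That a planned safety comparison is biased.* Sections 3.4 to 3.6 and 10.3 to 10.4 contain no safety endpoint and no between-arm comparison of adverse events. The exposure is to any later tabulation.
- *That every event judged unrelated vanishes.* Serious events, including unplanned admissions and emergency department visits, are reported whatever their cause. Fall-associated events are recorded without a causal test. Incidents have their own routes in 9.4. Whether an unrelated serious event also reaches the CRF cannot be settled, because neither the form nor the content of the Appendix 3 flow chart is available.
- *That excluding eye-drop blurriness is an error.* The exclusion is already limited by cause. Blur from lens rotation or macular oedema lies outside it.

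**Conclusion.** The point holds in a limited form. For non-serious, non-fall events, entry on the CRF depends on a judgement that the event is related to treatment. The protocol names no one to make that judgement, and those in a position to make it know or can learn the lens. An arm-by-arm table of these events could not be shown to be free of that influence, and the omitted events could not be recovered from the CRF. This rests on reading 9.3 literally and on the masking arrangements as written in 7.3 to 7.5.

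The direction and size of any bias are unknown, and the figures in the working are illustrations on assumed rates. The primary outcome analysis is not affected. This is a cheap improvement worth making, not a flaw that undermines the trial. The mismatches between 9.3, 9.4 and 13.9 are a separate administrative matter and stand on the text alone.

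**What to change.** 1. In 9.3, record on the CRF every ocular adverse event in either eye, every fall-associated event and every serious event, in both arms, from first-eye surgery to visit 3, whatever the suspected cause.
2. Ask the same adverse event question in both arms at visits 2 and 3, before the visual assessment. This fits the order that 7.4 already sets for the mobility tests. An assessor who did the visual assessment at visit 2 may already know the lens at visit 3, so the wording should be fixed in advance.
3. Keep relatedness as a separate field, completed after the event has been entered. The total count of ocular events then no longer depends on attribution, and unmasked opinion affects only the subset judged related.
4. Add to section 10 a descriptive table by arm of all ocular events alongside those judged related.
5. Reconcile 9.3, 9.4 and 13.9 on who assesses causality and seriousness, and on the time allowed for reporting to the sponsor.

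The cost is protocol wording and an adverse event page on the CRF. The downside is a few more minor ocular events to log. No extra visits or staff are needed.
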